10.6 Safety and Tolerability Assessments

10.6.1 Adverse events

Where changes in severity are recorded in the Case Report Form (CRF), each separate severity of the AE will be reported in the listings, only the most severe will be used in the summary tables. A pre-existing condition is defined as an AE that starts before the participant has provided written informed consent and is ongoing at consent. A non-treatment emergent AE is defined as an AE which starts after informed consent but prior to dosing, and that does not worsen postdose. A treatment-emergent AE is defined as an AE which occurs postdose or which is present prior to dosing and becomes more severe postdose.

All AEs will be listed. Treatment-emergent AEs will be summarized by treatment, severity and relationship to the study drug. The frequency (the number of AEs, the number of participants experiencing an AE and the percentage of participants experiencing an AE) of treatment-emergent AEs will be summarized by treatment, Medical Dictionary for Regulatory Activities (MedDRA) version 23.0 system organ class and preferred term. The summary and frequency AE tables will be presented for all causalities and those considered related to the study drug by the investigator. Any serious AEs will be listed.

The severity of infusion reactions will be graded using the table for assessing acute allergic reactions and events of cytokine release syndrome in protocol Section 6.1.1.2.; all other AEs will be graded for severity using the definitions of mild, moderate and severe provided in protocol Section 10.3.3. from the Division of Allergy and Infectious Diseases (DAIDS) Table for Grading the Severity of Adult and Pediatric Adverse Events, version 2.1 (July 2017).

Discontinuations of study intervention and/or of study due to AEs will be listed.

10.6.2 Medical history, pre-existing conditions, and prior medication

All medical history, pre-existing conditions and prior medication data will be listed.

10.6.3 Concomitant medication

Concomitant medication will be coded using the WHO drug dictionary (Version Global B3 202003 / WHODD MAR20B3). Concomitant medication will be listed.

10.6.4 Chest x-ray

All chest x-ray data will be listed.

10.6.5 Clinical laboratory parameters

All clinical chemistry and hematology data will be summarized by parameter and treatment together with changes from baseline, and listed. Baseline is defined as the Day 1 predose assessment. Additionally, clinical chemistry and hematology data outside the reference ranges will be listed and flagged on individual participant data listings.

All SARS-CoV-2 panel parameters (C-reactive protein, ferritin, D-dimer, procalcitonin, and troponin) will be summarised separately, together with changes from baseline, and listed. Baseline is defined as the Day 1 predose assessment. Additionally, SARS-CoV-2 panel data outside the reference ranges will be listed and flagged on individual participant data listings.

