9.4.2. Safety Analyses

Safety analyses will be conducted using the safety population described above.

All investigational product and protocol procedure AEs will be listed, and if the frequency of events allows, safety data will be summarized using descriptive methodology.

The incidence of AEs for each treatment will be presented by severity and by association with intervention as perceived by the investigator. Adverse events reported prior to randomization will be distinguished from those reported as new or increased in severity during the study post-randomization.

Safety parameters that will be assessed include, but are not limited to, safety laboratory parameters, and vital signs. The parameters will be summarized using standard descriptive statistics. Additional analysis will be performed if warranted upon review of the data.

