10.2. Appendix 2: Clinical Laboratory Tests

Clinical laboratory tests will be performed according to the SoA.

Additional tests may be performed at any time during the study as determined necessary by the investigator or required by local regulations.

Pregnancy testing will be performed according to the SoA.

Central and local laboratories will be used. The table below describes when the local or central laboratory will be used.

If the local laboratory results are used to make either a study intervention decision or response evaluation, the results must be recorded in the CRF.

Laboratory results that could unblind the study will not be reported to investigative sites or other blinded personnel.

Protocol-specific requirements for inclusion or exclusion of participants are detailed in Section 5 of the protocol.

Investigators must document their review of the laboratory safety report as described in Section 8.2.4.

Refer to Section 10.6 for recommended laboratory testing for hypersensitivity events.

Clinical Laboratory Tests	Comments
Hematology	Assayed by local laboratory
Hemoglobin	
Hematocrit	
Erythrocyte count (RBCs - Red Blood Cells)	
Mean cell volume	
Mean cell hemoglobin	
Leukocytes (WBCs - White Blood Cells)	
Differential	
Neutrophils, segmented	
Lymphocytes	
Monocytes	
Eosinophils	
Basophils	
Platelets	
Cell Morphology (RBC and WBC)	
Clinical Chemistry	Assayed by local laboratory
Sodium	
Potassium	
Chloride	
Bicarbonate	
Total bilirubin	
Direct bilirubin	Record on Day 1 and if abnormal values occur
Alkaline phosphatase (ALP)	
Alanine aminotransferase (ALT)	
Aspartate aminotransferase (AST)	
Gamma-glutamyl transferase (GGT)	Record on Day 1 and if abnormal values occur
Blood urea nitrogen (BUN)	
Creatinine	
Creatine kinase (CK)	Record on Day 1 and if abnormal values occur
Uric acid	Record on Day 1 and if abnormal values occur
Total protein	
Albumin	
Calcium	Record on Day 1 and if abnormal values occur
Phosphorus	Record on Day 1 and if abnormal values occur
Glucose	
Amylase	Record on Day 1 and if abnormal values occur
Lipase	Record on Day 1 and if abnormal values occur
Lactate dehydrogenase (LDH)	
Calculations	Completed locally
eGFR	calculated by CKD-EPI equation
SARS-Cov-2 viral infection determination	Local laboratory

Clinical Laboratory Tests	Comments
SARS-Cov-2 Panel	
C-Reactive Protein	
Ferritin	
D-dimer	
Procalcitonin	
Troponin	
SARS-Cov-2 viral infection confirmation	
Hormones (female)	Assayed by local laboratory.
Serum Pregnancy	

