8. SAMPLE SIZE JUSTIFICATION

For Cohorts 1-3, approximately 24 participants will be randomized to receive one of three dose levels of LY3819253 or placebo. Additional participants may be required to ensure a minimum of 8 participants in each cohort complete 7 days of study assessments. Up to a maximum of 3 additional participants per cohort may be added.

Participant viral loads over time were simulated using a representative PK/PD model to enable a Monte Carlo assessment of the power of the trial to detect a 30% treatment difference in mean AUC (28 day) of viral load. This assessment revealed greater than 90% probability of meeting the following Bayesian critical success factor:

Pr ((mean AUC_{PL} – mean AUC_{LY})/ mean AUC_{PL} > 0.3) > 0.60

PL = placebo, LY = LY3819253

Additionally, the anticipated 6 participants per treatment provides greater than 80% probability (within each treatment arm) of observing safety events of reasonable prevalence (that is, at least 25%) to support the primary objective of safety assessment.

For the optional Cohort 4, up to 100 participants may be randomized in an approximate 1:1 ratio to receive either LY3819253 or placebo. The overall numbers of participants randomized to LY3819253 and placebo in this study will provide 60% power to detect a reduction in the rate of clinical worsening from 22% to 9% (one-sided alpha=0.05). Clinical worsening is defined as the proportion (percentage) of participants with any worsening on the NIAID ordinal scale from baseline to Day 15.

A participant is only allowed to receive one IV infusion in one cohort.

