10. STATISTICAL METHODOLOGY

10.1 General

Data listings will be provided for all data that is databased. Summary statistics and statistical analysis will only be presented for data where detailed in this SAP. For continuous data, summary statistics will include the arithmetic mean, arithmetic standard deviation (SD), median, min, max and N; for log-normal data (e.g. the PK parameters: AUCs and maximum observed drug concentration $[C_{max}]$) the geometric mean and geometric coefficient of variation (CV%) will also be presented. For categorical and ordinal data, frequency count and percentages will be presented. Data listings will be provided for all participants up to the point of withdrawal, with any participants excluded from the relevant population highlighted. Summary statistics and statistical analyses will generally only be performed for participants included in the relevant analysis population. For the calculation of summary statistics and statistical analysis, unrounded data will be used.

Mean change from baseline is the mean of all individual participants' change from baseline values. Each individual change from baseline will be calculated by subtracting the individual participant's baseline value from the value at the timepoint. The individual participant's change from baseline values will be used to calculate the mean change from baseline using a SAS procedure such as Proc Univariate.

Data analysis will be performed using SAS[®] Version 9.4 or greater.

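### For eight chemistry analytes, the planned post-Day 1 means and changes from baseline rest on values that were recorded because they were abnormal

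*SAP*

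**What the plan says.** Protocol Appendix 2 (Section 10.2) lists the chemistry panel and states: "Clinical laboratory tests will be performed according to the SoA". The Schedule of Activities puts chemistry at screening, on Days 1, 3, 7, 11, 15, 22 and 29, at discharge or early discontinuation, and weekly for those still in hospital after Day 29. Eight chemistry rows in Appendix 2 carry the comment "Record on Day 1 and if abnormal values occur": direct bilirubin, GGT, creatine kinase, uric acid, calcium, phosphorus, amylase and lipase. The remaining chemistry rows, hematology and the SARS-CoV-2 panel carry no such comment.

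SAP 10.6.5 makes no distinction between these groups: "All clinical chemistry and hematology data will be summarized by parameter and treatment together with changes from baseline, and listed". It adds: "Baseline is defined as the Day 1 predose assessment". SAP 10.1 fixes the statistics: "For continuous data, summary statistics will include the arithmetic mean, arithmetic standard deviation (SD), median, min, max and N". It also says: "Mean change from baseline is the mean of all individual participants' change from baseline values". Protocol 9.4.2 is equally general about safety parameters: "The parameters will be summarized using standard descriptive statistics".

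None of these sections exempts the eight analytes or says how a result left unrecorded because it was normal is to be treated. SAP 12 reports no departure from the protocol's analyses.

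**The concern.** For the eight analytes, whether a post-Day 1 value exists in the database depends on the value itself. A mean or median at Day 7 therefore describes the participants who were abnormal at Day 7, not the arm. The mean change compares those participants' abnormal values with their own Day 1 values, so part of the change is produced by the selection. The gap cannot be treated as missing at random, because the reason for absence is the unobserved normal result.

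Safety is the primary objective, and SAP 10.6.11 plans no inferential safety analysis, so the descriptive tables and listings are the evidence. Creatine kinase, amylase and lipase are all among the restricted analytes. A table that can create a shift in an arm with no drug effect, and can shrink a true difference between arms, gives the reader no means of correcting it.

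**Working it through.** **Inputs from the documents.** Eight restricted rows (counted in Appendix 2). Baseline is Day 1 predose, recorded for all. The mean change is the mean of individual changes, so only participants with a recorded later value contribute. Six participants per active dose in Cohorts 1 to 3 come from SAP 8: "the anticipated 6 participants per treatment provides greater than 80% probability (within each treatment arm) of observing safety events". That section's own figure reproduces: for a 25% event, 1 − 0.75^6 = 0.822, above 80%. The plan states no figure on the present point.

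**Inputs assumed.** The documents give no abnormality rate, distribution or within-participant correlation. I take 2.5% to 50% abnormal per visit and correlations ρ of 0.3 to 0.8, with participants independent.

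**Step 1: how much data remains.** If only abnormal values are recorded at rate p, an arm of 6 has on average 6p values per visit, and the chance of none is (1 − p)^6.

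| p | expected values | chance of none |
|---|---|---|
| 2.5% | 0.15 | 0.859 |
| 10% | 0.6 | 0.531 |
| 25% | 1.5 | 0.178 |
| 50% | 3.0 | 0.016 |

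**Step 2: spurious change with no drug effect.** Take baseline and later values as bivariate normal in SD units, with a later value recorded only above an upper limit of 1.96. The true mean change is 0.

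- Population centred in the range: the recorded mean is φ(1.96)/(1 − Φ(1.96)) = 0.0584/0.0250 = 2.34. The recorded mean change is (1 − ρ) × 2.34, which is 0.47 at ρ = 0.8 and 1.64 at ρ = 0.3.
- Population already 1 SD high (about 17% recorded): the excess over the population mean is φ(0.96)/(1 − Φ(0.96)) = 0.2516/0.1685 = 1.49, so the recorded mean is 2.49 against a true 1.00. The recorded mean change is (1 − ρ) × 1.49, which is 0.30 to 1.05.
- Abnormal low only: by symmetry the same sizes with a negative sign.
- Centred population, abnormal equally often in both directions: the recorded mean and mean change are both about 0, but they describe only out-of-range participants.

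A simulation of 2,000,000 draws gave the same results to within 0.01 SD.

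**Step 3: shrinkage of a real difference.** Illustration only, for creatine kinase: log-normal, median 100, geometric SD 2 (log SD s = 0.693), upper limit 200, log-scale correlation 0.6.

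- No drug effect: 1 − Φ(1) = 15.9% are abnormal. The true mean is 100 × exp(s²/2) = 127. The recorded mean is 127.2 × Φ(s − 1)/0.159 = 127.2 × 0.3795/0.1587 = 304. The same participants' baseline mean is 127.2 × Φ(0.6s − 1)/0.159 = 127.2 × 0.2796/0.1587 = 224. The displayed change is 304 − 224 = +80, against a true 0.
- Every value doubled by the drug: the median is now 200, so 50% are abnormal. The recorded mean is 254.3 × Φ(s)/0.5 = 254.3 × 0.756/0.5, about 384. The displayed ratio of means is 384/304 = 1.26, against a true 2.0.

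In this example the proportion abnormal moves from 15.9% to 50% while the displayed mean rises by only a quarter. The count carries the signal that the selected mean loses.

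**The case against.** The strongest reply is that nothing needed to detect an individual abnormality is lost. SAP 10.6.5 lists and flags out-of-range chemistry results, which are the values the recording rule keeps. Protocol 8.2.4 sends clinically relevant laboratory changes to the adverse event page, and Protocol 9.5 has the independent safety committee review selected laboratory measurements unblinded. The tables also show N, so a drop after Day 1 would be visible. All of this stands. It limits the damage to the mean, median and change tables, but it does not make those tables interpretable: a small N shows that values are absent, not that they are absent because they were normal.

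The Appendix 2 wording also does not forbid entry of normal results, and it does not say what happens once an abnormality has occurred. That is true. If some sites enter normals and others do not, the summary mixes complete and selected data in unknown proportion.

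A reader might infer large rises in every arm. The documents do not support that. It follows only for analytes abnormal mainly on the high side; calcium, phosphorus and uric acid may be low as well, and the distortion can then reverse or cancel. A reader might also infer that hepatic signals become unreadable. They do not: ALT, AST, ALP and total bilirubin carry no restriction.

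Finally, the table shells are a separate document, and the text of SAP 14.3 on insufficient data was not available to me. Either could change how sparse tables are displayed, so I make no claim about their final layout.

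**Conclusion.** The recording rule and the summary rule do not fit together for eight analytes. Followed as written, the plan gives a complete Day 1 summary, followed by means, medians and changes from baseline selected on the outcome or drawn from an uncontrolled mix. This follows from the two texts and needs no assumption about rates.

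The size does need assumptions. Over abnormality rates of 2.5% to 50%, an arm of 6 has about 0.15 to 3 recorded values per visit, and 86% to 2% of visits have none. For an analyte abnormal on the high side, the spurious mean change is about 0.3 to 1.6 SD in the cases worked. The creatine kinase figures illustrate one set of inputs and are not an estimate for this trial.

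The scope is limited: descriptive tables for eight analytes, with no test, sample size or stated decision rule affected. It is worth correcting because the tables belong to the primary objective and the correction is cheap.

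**What to change.** In SAP 10.6.5, exclude the eight named analytes from the post-Day 1 mean and change-from-baseline tables. Report instead, by treatment:

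- the number and percentage of participants with at least one recorded post-dose value outside the reference range, high and low separately;
- the worst value as a multiple of the relevant limit;
- the existing listing with flags.

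Use as denominator the participants with at least one post-dose chemistry assessment, who can be identified from the unrestricted analytes. Simply counting every unrecorded value as not abnormal would treat missed visits, deaths and withdrawals as normal results. Add a footnote that unrecorded values at assessed visits are presumed normal or not tested. The cost is a few lines of SAP text and revised table shells, with no new data collection.

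Alternatively, remove the restriction in Appendix 2 so that all available results for the eight analytes are entered. The tables in SAP 10.6.5 can then stand, at the cost of a protocol change and some extra CRF entry.

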10.6.6 Vital signs

Vital signs data will be summarized by treatment together with changes from baseline, where baseline is defined as the Day 1 predose assessment. Figures of mean vital signs and mean changes from baseline profiles will be presented by treatment.

Values for individual participants will be listed.

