1.3. Schedule of Activities (SoA)

Assessments obtained previously as part of routine clinical care may be used as the baseline assessment as long as they were done no more than 48 hours before randomization.

Study J2W-MC-PYAA	Screening		Double-blind treatment and assessments									Follow-up if inpatient in hospital after Day 29	Post- treatment follow-up visit	
Study Day		1	2	3	4	7	11	15	22	29		Every 7 days until discharge or Day 60	60	
Visit window (± number of days)	-2						2	2	2	2	2	2	4	
Procedures														Comments
Informed Consent	Х													
Inclusion and exclusion criteria review	Х													
Demographics	Х													Including age, gender, race, ethnicity
Preexisting conditions and medical history	х													Obtained from interview or available information, and including timing of exposure and onset of symptoms suggestive of SARS-CoV-2 infection
Prior treatments of special interest within the last 2 weeks	Х													NSAIDs, antivirals, antibiotics, antimalarials, corticosteroids, cytokine- directed therapy or other investigational treatments.
Tobacco use		Х												Includes e-cigarettes.
Concomitant medications		Х	X	X	Х	X	X	Х	Х	Х	X	X	Х	
Adverse events (AEs)	X	X	X	X	X	X	X	X	X	X	X	X	X	Any events that occur after signing the informed consent are considered AEs as defined in Section 10.3.

Study J2W-MC-PYAA	Screening		Double-blind treatment and assessmentsDischargeFollow-up iffrominpatient intreatment inhospital orhospitalfoEDafter Day 29interval											
Study Day		1	2	3	4	7	11	15	22	29		Every 7 days until discharge or Day 60	60	
Visit window (± number of days)	-2						2	2	2	2	2	2	4	
Physical Evaluation of Physical examination	r Clinical As X	sessm	ents											Documentation of hospital-based exam is acceptable.
Symptom-directed physical exam		Х	X	Х	X	X	Х	Х	Х	Х	Х	Х		Documentation of hospital-based exam is acceptable.
Vital signs	Х	х	х	х	Х	х	Х	х	X	х	Х	Х	Х	 Documentation of hospital-based exam is acceptable. Includes: temperature, pulse rate, BP, respiratory rate, SpO2, and where applicable FiO2. Day 1 timing: immediately before the infusion, every 15 minutes during the infusion, as possible every 30 minutes for 2 hours after infusion and every 1 hour for the next 4 hours after infusion. Automation may be used. All other study days: once daily.
Single 12-lead ECG (local)	Х													Documentation of hospital-based exam within 72 hours prior to dosing is acceptable.

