5.2. Exclusion Criteria

Participants are excluded from the study if any of the following criteria apply:

Medical Conditions

- 10. Require invasive mechanical ventilation or anticipated impending need for invasive mechanical ventilation
- 11. Anticipate transfer to another hospital which is not a study site within 5 days of randomization

- 12. Have known allergies to any of the components used in the formulation of the interventions
- 13. Have hemodynamic instability requiring use of pressors within 24 hours of randomization
- 14. Were resident in a nursing home or long-term care facility immediately prior to current hospitalization
- 15. Suspected or proven serious, active bacterial, fungal, viral, or other infection (besides COVID-19) that in the opinion of the investigator could constitute a risk when taking intervention
- 16. Have any co-morbidity requiring surgery within <7 days, or that is considered life-threatening within 29 days
- 17. Have prior history of hepatic impairment, such as
 - a. severe liver cirrhosis Child-Pugh B or worse
 - b. cirrhosis with a history of hepatic encephalopathy
 - c. clinically meaningful ascites requiring ongoing treatment with diuretics and/or paracentesis, or
 - d. history of hepatorenal syndrome.
- 18. Have any serious concomitant systemic disorder that, in the opinion of the investigator, would preclude participation in the study
- 19. Current diagnosis of active malignancy that, in the opinion of the investigator, could constitute a risk when taking investigational product
- 20. Received convalescent COVID-19 plasma treatment prior to enrollment

Diagnostic assessments

- 21. Have an SpO2 <88% while breathing room air at rest. If on supplemental oxygen at the time of screening, use the last time point of measurement on room air up to 48 hours prior
- 22. This criterion was removed
- 23. Have alanine aminotransferase (ALT) or aspartate aminotransferase (AST) >5X upper limit of normal (ULN)
- 24. Have acute kidney disease with an eGFR <30 mL/min/1.73 m² based on the chronic kidney disease epidemiology collaboration equation (CKD-EPI). Chronic kidney disease is allowable, if judged to be stable for the past 3 months, in the opinion of the investigator.

Other Exclusions

- 25. Are pregnant or breast feeding
- 26. Are concurrently enrolled in any other type of medical research judged not to be scientifically or medically compatible with this study
- 27. Are Lilly employees

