8.2.2. Vital Signs

Vital signs will be measured as specified in the SoA and as clinically indicated. Vital signs include

- Body temperature
- Blood pressure
- Pulse rate
- Respiration rate
- Saturation of peripheral oxygen, and
- Supplemental oxygen flow rate, FiO2 if known, and method of delivery, if applicable.

Additional vital signs may be measured during the study if warranted, as determined by the investigator.

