8.2.7. Respiratory Support

Once enrolled in the study, participants may be managed with high-flow nasal cannula, noninvasive positive pressure ventilation or any other form respiratory support as needed per investigator discretion.

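### SAP 10.6.6 summarises SpO2 as a raw mean change without regard to concurrent oxygen support, so the safety summary can understate, cancel or reverse a respiratory decline

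*SAP*

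**What the plan says.** **Analysis.** SAP 10.6.6 reads: "Vital signs data will be summarized by treatment together with changes from baseline, where baseline is defined as the Day 1 predose assessment". It continues: "Figures of mean vital signs and mean changes from baseline profiles will be presented by treatment". SAP 10.1 gives the arithmetic: "Each individual change from baseline will be calculated by subtracting the individual" participant's baseline from the later value, with no adjustment. SAP 10.2 also summarises SpO2 among the baseline characteristics.

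**SpO2 is in scope.** The vital-signs row of the Schedule of Activities (Protocol 1.3) says: "Includes: temperature, pulse rate, BP, respiratory rate, SpO2, and where applicable FiO2". Protocol 8.2.2 adds to the same list: "Supplemental oxygen flow rate, FiO2 if known, and method of delivery, if applicable".

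**Support can change on study.** Under Protocol 8.2.7, once enrolled, "participants may be managed with high-flow nasal cannula, noninvasive positive pressure ventilation or any other form respiratory support", at the investigator's discretion.

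**Low baselines are eligible.** Exclusion 21 removes only those who "Have an SpO2 <88% while breathing room air at rest". For someone already on oxygen at screening, it relies on the most recent room-air reading.

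**No linking rule.** Neither document defines a room-air-only SpO2 summary, an SpO2/FiO2 ratio, a display by support level, or a rule for readings taken after support has changed.

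**The concern.** Supplemental oxygen is given to raise SpO2. After support is escalated, the reading reflects the oxygen delivered as well as the state of the lungs. A raw difference from the Day 1 predose value then mixes the two, and a mean over the arm inherits the mixture.

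The protocol itself reads oxygenation in context. Exclusion 21 and the severity definitions in Appendix 8 set SpO2 thresholds on room air, and Appendix 8 also uses a ratio to FiO2. The SAP summary drops that context.

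Three features raise the stakes within the safety analysis:

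- Safety is the primary objective, and Protocol 6.6.1 names vital signs among the data reviewed for dose escalation.
- Protocol 10.3.1 takes COVID-19 hypoxaemia needing oxygen, non-invasive ventilation or high flow, and respiratory failure needing invasive ventilation or ECMO, out of adverse event reporting unless the investigator attributes it to the intervention. Under 10.3.2, what is not an AE cannot be an SAE. AE tables therefore cannot be relied on to count respiratory deterioration.
- Oxygen and non-invasive ventilation are procedures of special interest (Protocol 8.2.6), and SAP 10.5.1 only lists those.

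**Working it through.** The plan states no figure on this point, so there is none to reproduce. The check is whether the planned statistic can move the wrong way, and under what condition.

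**1. One participant.** Reported change = SpO2 at visit − SpO2 at Day 1 predose. The values below are assumptions for illustration; 91% is above the 88% eligibility limit.

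- Day 1: 91% on room air (FiO2 0.21). Later visit: 95% on FiO2 0.60.
- Reported change: 95 − 91 = **+4 points**.
- SpO2/FiO2 at Day 1: 91 / 0.21 = 433. Later: 95 / 0.60 = 158.
- Change in ratio: 158 − 433 = −275, and 275 / 433 = **63% lower** (unrounded, 63.5%).

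The direction does not depend on the 0.60. With the same two SpO2 readings, the ratio is unchanged at FiO2 = 0.21 × 95 / 91 = 0.219 and falls at anything higher. At 0.5, the lower limit in the high-flow definition of Appendix 8, it is 95 / 0.5 = 190, which is 56% lower.

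**2. One arm.** Take n = 6, the planned number per dose (Protocol 9.2). Suppose k participants deteriorate, each from baseline B, and are brought to R on oxygen, while the others do not change. Then:

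- mean change as planned = k × (R − B) / n
- mean change had they stayed on room air = k × (−4) / n, assuming a fall of 4 points each

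With k = 2, the room-air equivalent is 2 × (−4) / 6 = −1.33 in every row. B, R, k and the 4-point fall are assumptions.

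| Baseline B (room air) | Reported mean, R = 94% | Reported mean, R = 96% |
|---|---|---|
| 90% | +1.33 | +2.00 |
| 92% | +0.67 | +1.33 |
| 94% | 0.00 | +0.67 |
| 96% | −0.67 | 0.00 |

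**3. Condition.** The reported change is positive when R > B, zero when R = B, and negative but smaller than the true fall when R is below B yet above the unsupported value. Apparent improvement is conditional. Some distortion occurs wherever oxygen raises the reading above what it would otherwise have been.

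**The case against.** **Oxygen data are vital signs too.** Protocol 8.2.2 places flow, FiO2 and delivery method in the vital-signs list, so SAP 10.6.6 read literally summarises them as well. This is partly right: the inputs are not discarded. But separate summaries do not link each SpO2 to its support. FiO2 is recorded only where applicable, so a participant who moves from room air to oxygen may have no baseline FiO2 and no computable change. Delivery method has no mean. The table shells that fix the layouts are not part of the documents.

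**Other summaries capture deterioration.** A reader might infer that respiratory harm is hidden by this plan. The documents do not support that. SAP 10.5.1 tabulates by treatment ICU admission, mechanical ventilation, any NIAID worsening to Day 15, NIAID worsening of at least 2 points at any time, and severity of shortness of breath. It also summarises NIAID, WHO and NEWS2 scores. Individual vital signs are listed, the ISAC reviews unblinded safety data, and no safety inference is planned (SAP 10.6.11). All this stands. What remains is that these summaries sit under efficacy, and none is a dedicated table of escalation to oxygen or non-invasive support. The scale categories are not printed, so how finely they register such escalation cannot be checked.

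**A rescued participant need not look better.** This is correct, as step 3 shows. Someone with a high baseline, or already on oxygen at Day 1, may show no change or a decline.

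**No reversal between arms is shown.** This is also correct. If a share p of an arm is rescued, with mean change g_R, and the rest change by g_S, the arm mean is g_S + p(g_R − g_S). If both arms have the same g values, they differ by (p_A − p_B)(g_R − g_S). The sign depends on whether rescued participants gain more than stable ones, and the documents give neither quantity.

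**Splitting SpO2 by post-dose support would create its own problem.** It would compare groups formed after randomisation, with about 6 participants per dose. This stands and shapes the fix.

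**Conclusion.** The point holds in a limited form. As written, SAP 10.6.6 yields an SpO2 table and figure that cannot be read as a respiratory safety measure. They can show a reduced decline, no change or a gain in participants whose support was escalated. In the illustration, a 63% fall in SpO2/FiO2 is recorded as +4 points. With 2 of 6 participants deteriorating, a room-air-equivalent mean of −1.33 is reported as anything from −0.67 to +2.00 over the assumed baselines and rescue levels.

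Those sizes rest on assumed readings. The mechanism rests only on the SAP text and on oxygen raising SpO2. The documents support neither a claim that the plan as a whole conceals respiratory harm nor a claim that the comparison between arms will reverse. The change is worth making because the AE exemption and the listing-only treatment of oxygen use leave the safety section without a dedicated by-treatment count of escalated support.

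**What to change.** Keep the planned SpO2 table and figure, and add the following to the SAP:

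1. **In 10.6.6, support level and escalation.** By visit and treatment, give the number of participants at each level (room air, supplemental oxygen, non-invasive ventilation or high flow, mechanical ventilation, ECMO). Also give the number with any escalation from the Day 1 predose level. Protocol 8.2.6 already records these requirements.
2. **In 10.6.6, change from baseline in SpO2/FiO2.** Set room air to 0.21. Where FiO2 is not recorded, use a flow-to-FiO2 conversion stated before the analysis, and report how many values rely on it.
3. **In 10.2, baseline SpO2 shown with baseline oxygen support.**

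Do not replace the overall table with treatment comparisons within post-dose support levels.

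The cost is SAP wording, an added table and summary, and an extra baseline line. No new data collection and no change to participant management are involved. Two limits should be stated with the results: FiO2 will be approximate for some participants, because the protocol records it only if known and gives no conversion; and the counts in Cohorts 1–3 will be small, although still readable as counts.
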